Subjects with QTc prolongation and symptoms must be monitored closely until the QTc elevation and symptoms have resolved. Study treatment may be restarted at a reduced dose level if all of the following conditions are met:

- Symptoms are determined to be unrelated to the QT interval prolongation
- Study treatment has been interrupted through a minimum of 1 week following the return of the QTcF to \leq 500 msec or return to \leq 60 ms above baseline.
- QT prolongation can be unequivocally associated with an event other than cabozantinib administration and is treatable/has been resolved
- Sponsor has reviewed all available information and has agreed to the continuation of study treatment

Following reinitiation of study treatment, ECGs must be repeated weekly for 2 weeks, then every 2 weeks for 1 month, then according to the protocol-defined time points.

All study treatment must be permanently discontinued if either of the following applies:

- Cardiac evaluation confirms that symptoms are the consequence of QT interval prolongation
- Recurrence of QTcF prolongation (confirmed by central ECG lab) after reinitiation of study treatment at a reduced dose

Hypophosphatemia

Hypophosphatemia has been reported during treatment with cabozantinib. Serum phosphorus should be monitored frequently while receiving cabozantinib. Other causes of hypophosphatemia should be ruled out and/or these causes treated in accordance to standard of care. Mild to moderate hypophosphatemia should be managed by oral replacement including food that are high in phosphate (diary items, meats, beans) and/or oral phosphate supplements in accordance to standard clinical practice guidelines.

Clinically relevant hypophosphatemia should be managed in accordance to the dose modification guidelines as outlined in the protocol.

Thyroid Function Disorders

Changes in thyroid function tests (TFTs) and hypothyroidism have been reported with cabozantinib therapy and other tyrosine kinase inhibitors as a result of altered thyroid hormone regulation by mechanisms that seem to be specific for each agent⁸⁶. Currently available data are insufficient to determine the mechanism of TFT alterations and its clinical relevance. Routine monitoring of thyroid function and assessments for signs and symptoms associated with thyroid dysfunction is recommended before initiation and during treatment with cabozantinib. Management of thyroid dysfunction (eg, symptomatic hypothyroidism) should follow accepted clinical practice guidelines and dose modification guidelines as outlined in the protocol.

Angioedema

Angioedema should be managed according to standard practice. The subject should be observed until symptoms resolve, with particular attention to maintaining an open airway.

Musculoskeletal and Connective Tissue Disorders

Cabozantinib appears to represent minimal risk of adverse musculoskeletal effects based on nonclinical GLP-compliant toxicology studies. The development of new or progressive, unexplained musculoskeletal symptoms such as pain or weakness should be assessed for underlying causes.

Rhabdomyolysis has been reported. Cabozantinib should be discontinued in subjects with serious and life-threatening rhabdomyolysis and interrupted if less severe forms occur when there are no other clear causes. Reinitiation of cabozantinib treatment must be discussed with and approved by the sponsor. Therapy of rhabdomyolysis should include supportive care and standard medical intervention.

Respiratory, Thoracic and Mediastinal Disorders

Dyspnea has been reported in clinical studies with cabozantinib. Symptoms should be managed according to locally accepted clinical practice including an assessment for underlying causes. Pulmonary embolism should be considered as possible causes for new onset dyspnea given the risk of thrombosis associated with inhibition of VEGF signaling. Furthermore, fistula formation and pneumonia have been reported in subjects treated with cabozantinib and should be considered as clinically indicated in subjects presenting with pulmonary symptoms.

Other

Treatment of emergent toxicities is at the investigator's discretion.

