- ❖ Nitrosoureas, nitrogen mustards, mitomycin C, at least 6 weeks prior to starting cabozantinib
- ❖ Autologous stem cell transplantation or autologous chimeric antigen receptor (CAR) T cell therapy at least 12 weeks prior to starting cabozantinib
- ❖ Allogeneic stem cell transplantation or allogeneic CAR T cell at least 24 weeks prior to starting cabozantinib, and these patients must also not have moderate to severe active acute or chronic graft versus host disease

7. Patients must be age 19 or older (state of Nebraska), because no dosing or adverse event data are currently available on the use of cabozantinib in patients <19 years of age.

8. Eastern Cooperative Oncology Group (ECOG) performance status of 0, 1, or 2; please see Appendix E)

9. Patients must have evidence of adequate bone marrow reserves, as defined by the following:

- ❖ Absolute neutrophil count (ANC) $\geq 1,000$ cells/mm³ without growth factors within 1 week of the initiation of treatment
- ❖ Total white blood cell count (WBC) $\geq 2,000$ cells/mm³ without growth factors within 1 week of the initiation of treatment
- ❖ Hemoglobin ≥ 8 g/dL without red blood cell transfusions within 2 weeks of the initiation of treatment
- ❖ Platelet counts of $\geq 100,000$ cells/mm³ for patients who have bone marrow plasmacytosis of <50%, or platelets $\geq 50,000$ cells/mm³ for patients who have bone marrow plasmacytosis of $\geq 50\%$

10. Patients must have evidence of adequate hepatic function, as defined by the following:

- ❖ Total bilirubin ≤ 1.5 times the upper limit of the institutional normal values
- ❖ Total AST (SGOT) and ALT (SGPT) ≤ 2.5 times the upper limit of the institutional normal values

11. Patients must have evidence of adequate renal function, as defined by the following:

- ❖ Serum creatinine within the institutional normal limits, OR if the creatinine is elevated

- ❖ Creatinine clearance (CrCl) ≥ 30 mL/min., as measured by a 24-hour urine collection, or estimated by the Cockcroft and Gault formula:

$$\text{Female CrCl} = \frac{(140 - \text{age in years}) \times \text{weight in kg} \times 0.85}{72 \times \text{serum creatinine in mg/dL}}$$

$$\text{Male CrCl} = \frac{(140 - \text{age in years}) \times \text{weight in kg} \times 1.00}{72 \times \text{serum creatinine in mg/dL}}$$

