5.7. DOSING DELAYS / DOSE MODIFICATIONS

In Phase I of this study we will determine the MTD among three doses. DLTs will be based solely on adverse events that occur during cycle 1. The definition of DLT includes:

- a. Any non-hematological toxicity Grade ≥ 3 , except for alopecia and nausea uncontrolled by medical management.
- b. Grade 4 neutropenia lasting more than 5 days.
- c. Febrile neutropenia of any duration (ANC $<1.0 \times 10^9/L$ fever $\geq 38.5^{\circ}\text{C}$)
- d. Grade 4 thrombocytopenia, or Grade 3 thrombocytopenia with bleeding, or any requirement for platelet transfusion
- e. Grade 4 anemia, unexplained by underlying disease.

We will study three dose levels using the 3+3 algorithm, so that we will accrue a minimum of 3 patients and a maximum of 18 patients in Phase I. The initial dose of cabozantinib for all patients treated on this study will be 20 mg P.O. daily, which is designated dose level -1. In the event that dose modifications are needed for toxicities, the following additional dose levels will be used:

Dose Level	Cabozantinib Dose
-1	20 mg p.o., daily
0	40 mg p.o., daily
+1	60 mg p.o., daily

To allow for optimal experimental design, capped dose of carfilzomib of 27 mg/m^2 will be used in the study without dose escalations or de-escalations. Given the potential for compounding/worsening toxicities with the addition of cabozantinib to carfilzomib, patients eligible for the trial will have to have had very good tolerance to carfilzomib in the context of treatment regimens they were receiving, with resolved prior carfilzomib toxicities to grade 1 or better, and no toxicities due to carfilzomib that required dose reductions to less than 27 mg/m^2 as dose adjustments will be allowed in the cabozantinib only. Stopping of carfilzomib however will be allowed if the adverse events secondary to carfilzomib that require its stopping are observed/met.

Specific dose modifications guidelines will be followed for the adverse events nausea, vomiting, diarrhea, neutropenia, and thrombocytopenia, and are detailed below. If a patient experiences several adverse events and there are conflicting recommendations, the investigator should use the recommended dose adjustment that reduces the dose to the lowest level.

Event Name	Diarrhea
Grade of Event	Management/Next Dose for Cabozantinib
\leq Grade 1	No change in dose
Grade 2	Hold until \leq Grade 1. Resume at same dose level.

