Grade 3	Hematologic (neutropenia, thrombocytopenia, anemia)	
Withhold carfilzomib dose.
 
If fully recovered before next scheduled dose, continue at same dose level.
 
If recovered to Grade 2 neutropenia or Grade 3 thrombocytopenia, reduce dose by one dose level: from 27 mg/m² to 20 mg/m², OR from 20 mg/m² to 15 mg/m².
 
If tolerated, the reduced dose may be escalated to the previous dose at the discretion of the physician.
 
TMA: If TMA is suspected, hold carfilzomib and manage per standard of care. If TMA is confirmed and related to carfilzomib, permanently discontinue carfilzomib. If TMA is excluded, may restart carfilzomib.
	
Withhold cabozantinib.
 
If the relevant lab value recovers to: $1.0 \times 10^9/L$ for ANC, 8 g/dL for hemoglobin, or $50 \times 10^9/L$ for platelets, resume cabozantinib treatment at same dose level. If the relevant lab value takes more than 3 weeks to recover to the level described above, restart cabozantinib administration at the next lower dose. If a second hold is required for the same event, administer cabozantinib at the next lower dose for subsequent cycles (for those subjects starting at 40 mg dose, cabozantinib would be discontinued if second hold required).

	Hepatic Toxicity	
25% dose reduction in case of baseline or treatment emergent mild or moderate hepatic impairment. Withhold carfilzomib until resolved or returned to baseline. After resolution, consider if restarting is appropriate. May be restarted at the dose (from 27 mg/m² to 20 mg/m², OR from 20 mg/m² to 15 mg/m²) with frequent monitoring of liver function. If tolerated, the reduced dose may be escalated to the previous dose at the discretion of the physician. Monitor liver enzymes regularly, regardless of baseline values, and modify dose based on toxicity.
	

Event Grade (NCI CTC V4.03) and Category		Action by Agent	
Grade	Adverse Event	Carfilzomib	Cabozantinib
	Renal	Serum creatinine ≥ 2 times baseline, CrCl < 15 mL/minute or CrCl decreases to $\leq 50\%$ of baseline, or patient requires dialysis: Withhold dose and monitor renal function. If renal toxicity is due to carfilzomib, resume dosing when renal function has improved to within 25% of baseline; resume with a reduced dose by 1 dose level.	

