Grade 4	Non-hematologic (including hemorrhage and peripheral neuropathy)	Withhold carfilzomib until resolved or returned to baseline. Consider restarting at the next scheduled treatment with one dose level reduction (from 27 mg/m ² to 20 mg/m ² , OR from 20 mg/m ² to 15 mg/m ²). If tolerated, the reduced dose may be escalated to the previous dose at the discretion of the physician.	Withhold cabozantinib until recovery to Grade 1 or screening value. Consult with the Medical Monitor or designee prior to restarting cabozantinib. If the Investigator and Medical Monitor concur, administer cabozantinib at the next lower dose for subsequent cycles, unless further dose reduction is required. If a second hold is required for the same event, administer cabozantinib at lower dose for subsequent cycles. For those subjects starting at 40 mg dose, cabozantinib would be discontinued if second hold required.
	Hematologic (neutropenia, thrombocytopenia, anemia, febrile neutropenia)	Hold drug. If fully recovered before next scheduled dose, continue carfilzomib at same dose level. If recovered to Grade 2 neutropenia or Grade 3 thrombocytopenia, reduce dose by one dose level (from 27 mg/m ² to 20 mg/m ² , OR from 20 mg/m ² to 15 mg/m ²). If tolerated, the reduced dose may be escalated to the previous dose at the discretion of the physician.	Withhold cabozantinib. If the relevant lab value recovers to: 1.0×10 ⁹ /L for ANC, 8 g/dL for hemoglobin, or 50×10 ⁹ /L for platelets, resume treatment at next lower dose for subsequent cycles, unless further dose reduction is required.
Permanently discontinue for any of the following		1. Hypertensive crisis 2. Hypertensive emergency 3. Malignant hypertension	1. Development of visceral perforation or fistula formation 2. Severe hemorrhage 3. Serious arterial thromboembolic event (e.g., myocardial infarction, cerebral infarction) 4. Nephrotic syndrome

Event Grade (NCI CTC V4.03) and Category		Action by Agent	
Grade	Adverse Event	Carfilzomib	Cabozantinib
			
5. Malignant hypertension, hypertensive crisis, persistent uncontrolled hypertension despite optimal medical management
 
6. Osteonecrosis of the jaw
 
7. Reversible posterior leukoencephalopathy syndrome.

	Hepatitis B reactivation	Any subject who becomes HBV DNA positive or develops reactivation of HBV should have carfilzomib treatment interrupted and receive appropriate anti-viral treatment as per a specialist in Hepatitis B.	

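### Section 5.7 bars the carfilzomib reductions that Table 5-1 prescribes, and the table's Grade 3 platelet recovery level is the same grade that triggered the hold

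*Combined protocol and SAP*

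**What the plan says.** Section 5.7 states that carfilzomib 27 mg/m² "will be used in the study without dose escalations or de-escalations". It then justifies requiring prior tolerance of that dose on the ground that patients must not have needed less, "as dose adjustments will be allowed in the cabozantinib only". The only carfilzomib change it goes on to permit is stopping for carfilzomib-related adverse events.

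Table 5-1 in Section 5.7.1 covers both drugs and gives carfilzomib two downward steps, 27 to 20 and 20 to 15 mg/m², in many rows. It also allows a return to the previous dose if the lower one is tolerated.

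For a Grade 3 hematologic event, thrombocytopenia included, the carfilzomib cell has three parts:

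- The drug is held at the outset.
- A complete return to normal leaves the dose unchanged: "If fully recovered before next scheduled dose, continue at same dose level".
- A partial return brings one of the two downward steps just described. The condition for it is worded as follows: "If recovered to Grade 2 neutropenia or Grade 3 thrombocytopenia, reduce dose by one dose level: from 27".

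In the same row cabozantinib is also withheld. Once the count reaches 50 × 10⁹/L "for platelets, resume cabozantinib treatment at same dose level".

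The Grade 4 hematologic row uses nearly the same carfilzomib sentence: "If recovered to Grade 2 neutropenia or Grade 3 thrombocytopenia, reduce dose by one dose level (from 27" mg/m² and so on.

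**The concern.** There are two faults, and the first is the larger.

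First, Section 5.7 and Table 5-1 give opposite instructions on whether carfilzomib may be reduced at all. This reaches every carfilzomib reduction in the table, not only the platelet rule.

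Second, a patient whose carfilzomib is withheld for grade 3 platelets is told to restart one level lower on having recovered to grade 3 platelets. That describes no recovery. Some sites may restart at the next scheduled dose. Others may assume that real improvement was meant and keep holding.

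Between them, the two faults let sites acting in good faith give 20 mg/m², 27 mg/m² or nothing at the same platelet count. That affects dosing safety and whether patients at the two institutions receive the same regimen.

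**Working it through.** The plan states no figure to reproduce on this point. The check is a comparison of texts, followed by illustrative arithmetic.

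**Step 1. May carfilzomib be reduced?**

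| Source | Permitted carfilzomib change |
|---|---|
| Section 5.7 | None, except stopping |
| Table 5-1 | 27 → 20 → 15 mg/m², with return to the previous dose |

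The phrase about no escalation or de-escalation might, alone, refer only to the phase I dose levels. The later clause confining adjustments to cabozantinib closes that route, because it is the stated reason for the tolerance requirement. Section 5.7's rule to choose the lowest recommended dose does not help either. It applies when several adverse events in one patient give conflicting advice, not when two rules for one event disagree.

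**Step 2. How much improvement comes before a reduced restart?**

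| Row of Table 5-1 | Neutropenia | Thrombocytopenia |
|---|---|---|
| Grade 3 | 3 → 2 (one grade) | 3 → 3 (none) |
| Grade 4 | 4 → 2 (two grades) | 4 → 3 (one grade) |

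Only one of the four cells requires no improvement. The near-identical Grade 4 sentence suggests that the wording was carried across, but the documents do not say so.

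**Step 3. Illustrative size.** Carfilzomib is given on days 1, 2, 8, 9, 15 and 16 (Section 8.2.4), so a planned cycle is 6 × 27 = 162 mg/m². Assume one hold, one reduction, and grade 3 platelets persisting through day 16. In each cell the first figure omits only the trigger-day dose and the second omits both doses that week.

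| Trigger | Restart at 20 | Held, or stopped | Restart at 27 | Gap, 20 versus held |
|---|---|---|---|---|
| Day 8 | 54 + 3×20 = 114; 54 + 2×20 = 94 | 2×27 = 54 | 54 + 3×27 = 135; 54 + 2×27 = 108 | 60; 40 |
| Day 15 | 108 + 20 = 128; 108 | 4×27 = 108 | 108 + 27 = 135; 108 | 20; 0 |

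As shares of plan, the day 8 gaps are 60/162 = 37% and 40/162 = 25%. The day 15 gaps are 20/162 = 12% and 0%. Restarting at 27 rather than 20 adds 135 − 114 = 21 or 108 − 94 = 14 mg/m² after a day 8 trigger, and 135 − 128 = 7 or 0 after a day 15 trigger.

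Beyond the trigger cycle, a full cycle at 20 mg/m² is 6 × 20 = 120 (120/162 = 74% of plan). At 15 mg/m² it is 6 × 15 = 90 (90/162 = 56%).

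**The case against.** The best defence is that the Grade 3 cell is a sequence. A dose is withheld first, and status is then judged before the next scheduled dose. Full recovery keeps the dose, and anything short of that at grade 3 brings a reduction. This is a sensible rule and probably the intended one. It stands, and it confines the platelet fault to one badly chosen word.

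It also answers a stronger reading that a reader might infer, namely that the table lets carfilzomib carry on with no interruption at an unsafe count. The documents do not support that. A dose is omitted first, and cabozantinib stays off until 50 × 10⁹/L.

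Nor do the different platelet levels for the two drugs prove a mistake. In the Grade 4 row, too, carfilzomib may restart at grade 3 while cabozantinib waits for 50 × 10⁹/L. Reduced dosing through stable grade 3 platelets is a defensible clinical choice, since inclusion criterion 9 admits patients at 50,000/mm³ when marrow plasmacytosis is at least 50%.

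On the wider conflict, Section 5.7 itself promises specific guidance for thrombocytopenia. Only Table 5-1 supplies it, under a title that names both drugs. Section 8.2.4 describes 27 mg/m² as a capped starting dose, which hints that later doses may be lower. These points make the table the likelier authority. They do not remove the sentence confining adjustments to cabozantinib, so a site that follows Section 5.7 is also following the protocol.

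**Conclusion.** The point holds as a minor one. Section 5.7 and Table 5-1 contradict each other on carfilzomib reduction, and the Grade 3 platelet condition needs rewording even if the sequential reading was meant.

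The effect is limited to dosing consistency and safety. A reader might infer that DLT counts or the choice of MTD are compromised by the wording. The documents do not support that: Section 5.7 counts grade 4 thrombocytopenia as a DLT, and otherwise only "Grade 3 thrombocytopenia with bleeding, or any requirement for platelet transfusion". Uncomplicated grade 3 thrombocytopenia is therefore not one. No sample size, power or alpha depends on the rule.

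The gaps of 0 to 60 mg/m² (0% to 37% of a cycle) between a reduced restart and a continued hold are illustrative. They rest on the assumed trigger day and on grade 3 platelets lasting through day 16. How many patients would be affected cannot be estimated from the documents.

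**What to change.** **(a) Section 5.7.** After the statement of no de-escalation, add *except the carfilzomib reductions in Table 5-1*. Change the clause confining adjustments to cabozantinib so that it agrees. The exception should also cover the table's return to the previous dose.

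**(b) Table 5-1, Grade 3 hematologic row, carfilzomib cell.** For platelets, drop the word for recovery and write: *Omit the dose; if platelets are still grade 3 and not worse at the next scheduled dose, give one dose level lower.*

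The cost is two phrases and one sentence, with no added patients or data. The present cell already calls for a judgement before the next scheduled dose.

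**If the sponsor wants a stricter floor**, for example the 50 × 10⁹/L used for cabozantinib, it must go into both the Grade 3 and the Grade 4 rows. Tightening the Grade 3 row alone would let a patient who fell to grade 4 restart at grade 3, while one who fell only to grade 3 had to wait for a higher count. This option assumes that 50 × 10⁹/L is the boundary between grades 2 and 3, since the documents do not print the CTCAE cut-offs. Its price is longer carfilzomib holds and lower exposure, mainly in patients with heavy marrow infiltration who enter near 50,000/mm³. That is a clinical trade-off for the sponsor's medical lead.

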14. The subject has experienced any of the following:

- ❖ clinically-significant GI bleeding within 6 months before the first dose of study treatment;
- ❖ GI disorders particularly those associated with a high risk of perforation or fistula formation including:
 - Tumors invading the GI tract, active peptic ulcer disease, inflammatory bowel disease (eg, Crohn's disease), diverticulitis, cholecystitis, symptomatic cholangitis or appendicitis, acute pancreatitis or acute obstruction of the pancreatic duct or common bile duct, or gastric outlet obstruction
 - Abdominal fistula, GI perforation, bowel obstruction, intra-abdominal abscess within 6 months before randomization,

Note: Complete healing of an intra-abdominal abscess must be confirmed prior to randomization

- ❖ hemoptysis of ≥ 0.5 teaspoon (2.5ml) of red blood within 3 months before the first dose of study treatment;
- ❖ any other signs indicative of pulmonary hemorrhage within 3 months before the first dose of study treatment.
- ❖ Patient who have developed or have had history of pulmonary hemorrhage while on carfilzomib will be excluded (fatal pulmonary hemorrhage has been observed with carfilzomib).

15. The subject has radiographic evidence of cavitating pulmonary lesion(s);

16. The subject has tumor invading or encasing any major blood vessels;

17. The subject has evidence of tumor invading the GI tract (esophagus, stomach, small or large bowel, rectum or anus), or any evidence of endotracheal or endobronchial tumor within 28 days before the first dose of cabozantinib;

18. Corrected QT interval calculated by the Fridericia formula (QTcF) > 500 ms per electrocardiogram (ECG) within 14 days before first dose of study treatment *Note: If a single ECG shows a QTcF with an absolute value > 500 ms, two additional ECGs at intervals of approximately 3 min must be performed within 30 min after the initial ECG, and the average of these three consecutive results for QTcF will be used to determine eligibility.*

19. Inability to swallow intact tablets

20. The subject has prothrombin time (PT)/INR or partial thromboplastin time (PTT) test $\geq 1.3 \times$ the laboratory ULN within 7 days before the first dose of study treatment;

21. Concomitant anticoagulation at therapeutic doses with oral anticoagulants (eg, warfarin, direct thrombin and Factor Xa inhibitors) or platelet inhibitors (eg, clopidogrel);

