Palmar-plantar erythrodysesthesia syndrome (PPES) occurred in 50% of patients treated with cabozantinib and was severe (Grade 3) in 13% of patients. Cabozantinib should be withheld in patients who develop intolerable Grade 2 PPES or Grade 3-4 PPES until improvement to Grade 1 when it can be resumed at a reduced dose.

Proteinuria:

Proteinuria was observed in 4 (2%) of patients receiving cabozantinib, including one with nephrotic syndrome, as compared to none of the patients receiving placebo. Urine protein should be monitored regularly during cabozantinib treatment and treatment **discontinued in patients who develop nephrotic syndrome.**

Reversible Posterior Leukoencephalopathy Syndrome:

Reversible Posterior Leukoencephalopathy Syndrome (RPLS), a syndrome of subcortical vasogenic edema diagnosed by characteristic finding on MRI, occurred in one (<1%) patient. An evaluation for RPLS should be performed in any patient presenting with seizures, headache, visual disturbances, confusion or altered mental function. **Discontinuation of cabozantinib should occur in patients who develop RPLS.**

Corrected QTc Prolongation

Cardiac arrest within 1 day of carfilzomib administration has been reported. If there is QT prolongation, we will consider holding carfilzomib.

If at any time on study there is an increase in QTcF to an absolute value > 500 ms or an increase of > 60 ms above baseline, two additional ECGs must be performed with intervals not less than 3 min apart within 30 min after the initial ECG.

If the average QTcF from the three ECGs is > 500 ms or increased by > 60 ms above baseline, the following actions must be taken:

- Interrupt study treatment
- Hospitalize symptomatic subjects (eg, with palpitations, dizziness, syncope, orthostatic hypotension, a significant ventricular arrhythmia on ECG) for a thorough cardiology evaluation and management
- Consider cardiology consultation for asymptomatic subjects for evaluation and management
- Check electrolytes, especially magnesium, potassium and calcium; correct abnormalities as clinically indicated
- Check concomitant medications for any medication that may have contributed to QT prolongation, and if possible, discontinue these medications (<http://www.qtdrugs.org>)
- Repeat ECG triplicates hourly until the average QTcF is ≤ 500 msec and the average increase is ≤ 60 ms above baseline, or otherwise determined by consultation with a cardiologist or appropriate expert.

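### The QTc restart rule accepts recovery below either limit, so a patient who crossed both can start the one-week restart clock while interruption is still mandatory

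*Combined protocol and SAP*

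**What the plan says.** The block on corrected QTc prolongation in Section 5.7.1 contains three rules on the same two limits.

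- **Interruption.** Study treatment must be interrupted "If the average QTcF from the three ECGs is > 500 ms or increased by > 60 ms above baseline". Crossing either limit is enough.
- **Monitoring after interruption.** "Repeat ECG triplicates hourly until the average QTcF is ≤ 500 msec and the average increase is ≤ 60 ms above baseline", unless a cardiologist or other suitable expert decides otherwise. Both limits must be met.
- **Restart.** Treatment may resume at a reduced dose if four conditions all hold. One is at least a week off treatment after "return of the QTcF to \leq 500 msec or return to \leq 60 ms above baseline". Either limit is enough.

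The other three restart conditions are that the symptoms are unrelated to the QT prolongation, that "QT prolongation can be unequivocally associated with an event other than cabozantinib administration and is treatable/has been resolved", and that "Sponsor has reviewed all available information and has agreed to the continuation of study treatment". After restart, "Following reinitiation of study treatment, ECGs must be repeated weekly for 2 weeks, then every 2 weeks for 1 month".

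At entry, Section 3.2 item 18 excludes only "Corrected QT interval calculated by the Fridericia formula (QTcF) > 500 ms per electrocardiogram (ECG) within 14 days before first dose of study treatment", so a baseline of up to 500 ms is eligible.

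**The concern.** The opposite of exceeding A or B is being within both A and B. The monitoring rule follows that logic and the restart rule does not, so the same block defines recovery in two ways. A patient who crossed both limits and has come back under only one satisfies the restart wording while still meeting the condition that made interruption mandatory.

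What is at stake is dosing a patient whose QTcF is still prolonged. QTc prolongation is on the list of cabozantinib events of particular interest (Section 8.1.7), and Section 5.7.1 notes reports of cardiac arrest within a day of carfilzomib. The restart text asks for no ECG at the moment of restart. The first one it requires comes about a week later, after up to 7 daily cabozantinib doses.

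**Working it through.** **Inputs.** The limits of 500 ms and 60 ms above baseline, and the *or*/*and* wording, come from Section 5.7.1. The highest eligible baseline, 500 ms, comes from Section 3.2 item 18. The individual baselines and QTcF values below are assumed for illustration, because the documents give no QTcF distribution. The plan states no figure of its own on this point to reproduce.

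**Rules.** Let b be the baseline QTcF and Q the current average, in ms.

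- Interruption required: Q > 500 or Q − b > 60, which is Q > min(500, b + 60).
- Restart clock as written: Q ≤ 500 or Q − b ≤ 60, which is Q ≤ max(500, b + 60).
- Restart clock with *and*: Q ≤ 500 and Q − b ≤ 60, which is Q ≤ min(500, b + 60).

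A patient has crossed both limits once Q > max(500, b + 60). On the way down, the first two rules are true together when

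min(500, b + 60) < Q ≤ max(500, b + 60),

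a band of width |500 − (b + 60)| = |440 − b| ms.

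| Baseline b (ms) | b + 60 (ms) | Clock can start while interruption is required, as written (ms) | Width (ms) | Overlap with *and* (ms) |
|---|---|---|---|---|
| 400 | 460 | 461–500 | 40 | 0 |
| 420 | 480 | 481–500 | 20 | 0 |
| 440 | 500 | none | 0 | 0 |
| 460 | 520 | 501–520 | 20 | 0 |
| 480 | 540 | 501–540 | 40 | 0 |
| 500 | 560 | 501–560 | 60 | 0 |

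These bands were confirmed by enumeration in 1 ms steps. With *and*, the restart rule is the exact complement of the interruption rule, so the overlap is empty at every baseline.

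**Two patients.**

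- Baseline 420, peak 520 (rise 100, both limits crossed), now 490. The 500 ms limit is met, so the clock starts. The rise is 490 − 420 = 70 ms, which exceeds 60, so interruption is still required.
- Baseline 460, peak 530 (rise 70, both limits crossed), now 515. The rise is 515 − 460 = 55 ms, so the clock starts. QTcF is still above 500 ms, so interruption is still required.

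Below a baseline of 440 ms the unmet limit is the rise from baseline; above 440 ms it is the absolute value. Entry is open on both sides.

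**The case against.** The strongest reply is that starting a clock is not an exposure. The patient is off treatment and must stay off for a week. If QTcF falls steadily through both limits, the only effect is that the week begins earlier. The hourly ECGs are mandatory until both limits are met, and the only exit is expert advice. The interruption rule applies at any time on study, so the permissive restart text can be read as never allowing a dose to someone known to be over a limit. Restart also needs a cause unequivocally other than cabozantinib, sponsor agreement and a reduced dose. A patient on 20 mg, the lowest level in Section 5.7, has no lower listed level. If the restart falls on day 1 of an early cycle, Section 5.2.3 and Table 7.1 may supply an ECG before dosing.

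Most of this stands as a limit on the consequence. To be exposed, a patient must have crossed both limits, probably had the hourly series ended early, and stayed between the limits for the week. It does not remove the defect. The clock condition is the only restart condition that states a QTcF value. The cause condition accepts a cause or prolongation that is merely treatable, and sponsor agreement carries no ECG criterion. A mid-cycle restart has no scheduled ECG before dosing, and beyond cycle 3 routine ECGs are every 12 weeks.

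The word *return* also supports reading the clause as referring to whichever limit was crossed. That handles every patient who crossed one limit, and no fault is claimed there. For a patient who crossed both, it does not say which limit governs.

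**Conclusion.** The concern holds. For a patient who crossed both limits, the restart wording and the interruption rule conflict over a band |440 − baseline| ms wide: nothing at a baseline of 440 ms, 20 ms at 420 or 460, and 60 ms at the eligibility ceiling of 500. This rests only on the protocol's own limits and on reading *or* as written.

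The widths are ranges of QTcF, not shares of patients. No frequency can be given, and with a total accrual target of 32 (Section 10.3) the number affected is likely to be small. No endpoint analysis, sample size, alpha or power is touched. It should still be corrected, because it is a safety rule on which two adjacent instructions disagree.

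**What to change.** In the restart condition of Section 5.7.1, start the one-week interval only once the average QTcF is at or below 500 ms *and* no more than 60 ms above baseline, matching the hourly-ECG instruction. Both limits keep their present values.

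The cost is a few words in a protocol amendment, with no new procedure. Some interruptions will last longer, and a patient who settles between the two limits will not be able to restart. The interruption rule already implies that outcome.
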